6.2 ECOG Performance Status Score

The ECOG performance status score has a range from 0 (Fully active; able to carry on all pre-disease performance without restriction) to 5 (Dead). The baseline ECOG performance status is summarized in the disease-specific baseline characteristics as specified in Section 5.2. A listing of ECOG performance status will be provided.

6.3 Changes from Protocol-Specified Efficacy Analysis

Analysis and summary will not be provided for time to duration of response and progression-free

survival due to limitation of the data.

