6.7 Blinding

Blinding and breaking the blind are not applicable as this study is open label.

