9.4.2 Efficacy Analyses

The ORR will be summarized with frequencies and percentages with 90% CI by each dose/cohort. The duration of response (DOR) for complete response (CR) and partial response (PR) patients and PFS for all treated patients will be summarized with descriptive statistics (N, arithmetic mean, SD, median, minimum, and maximum). The ORR, DOR, and PFS will

be determined using RECIST v1.1. Kaplan-Meier methodology will be used to estimate median DOR and PFS and corresponding 95% CI.

ORR, DOR, and PFS are defined below.

ORR: defined as the total number of patients with confirmed responses of either CR or PR per RECIST v1.1 divided by the total number of patients who are evaluable for a response.

DOR: defined as the time from onset of response (CR or PR) that is subsequently confirmed to the first observation of progressive disease or death due to any cause. Patients who are alive and progression-free at the time of data analysis will be censored at the time of their last assessment for tumor response.

PFS: defined as the time from the patient's first dose to the first observation of progressive disease or death due to any cause. Patients who are alive and progression-free at the time of data analysis will be censored at the time of their last assessment for tumor response.

More details of censoring rule for DOR and PFS will be outlined in SAP.

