BOR	Best Overall Response
CI	Confidence Interval
CR	Complete Response
CSR	Clinical Study Report
CTCAE	Common Toxicity Criteria for Adverse Events
DLT	Dose-Limiting Toxicity
DOR	Duration of Response
ECG	Electrocardiogram
ECOG	Eastern Cooperative Oncology Group
GC	Gastroesophageal Cancer
GI	Gastrointestinal
HR	Hazard Ratio
IHC	Immunohistochemistry
ITT	Intent to Treat
IV	Intravenous
LTFU	Long Term Follow-up
MedDRA	Medical Dictionary for Regulatory Activities
MTD	Maximum Tolerated Dose
NCI	National Cancer Institute
NE	Not Estimable
ORR	Objective Response Rate
OS	Overall Survival
PD-1	Programmed cell Death protein 1
PFS	Progression-Free Survival
PK	Pharmacokinetics
PR	Partial Response
PT	Preferred Term
Q1, Q3	First Quartile, Third Quartile
RD	Recommended Dose
RECIST	Response Evaluation Criteria in Solid Tumors
SAE	Serious Adverse Event
SAP	Statistical Analysis Plan

FPA150-001 Statistical Analysis Plan

Version 1.0, 1 September 2021

SE	Standard Error
SOC	System Organ Class
StD	Standard Deviation
TEAE	Treatment-Emergent Adverse Event
TFLs	Tables, Figures, and Listings
WHO	World Health Organization
WHO-DD	World Health Organization Drug Dictionary

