1 BACKGROUND AND RATIONALE

This statistical analysis plan (SAP) describes the statistical analysis methods and data presentations to be used in tables, figures and listings (TFLs) of the final analysis in the clinical study report (CSR) for study FPA150-001. This SAP is based on the study protocol Amendment 2 dated 04 February 2019. The SAP will be finalized prior to data finalization for the final analysis.

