1.2.2 Phase 1b Objectives and Endpoints

[figure not shown]

The objectives and endpoints for Phase 1b of the study are summarized in Table 6.

Table 6: Objectives and Endpoints: Phase 1b

OBJECTIVES	ENDPOINTS
PRIMARY - SAFETY	
FPA150 Monotherapy 
 To evaluate the safety and tolerability of FPA150 as monotherapy in patients with B7-H4+ advanced solid tumors treated at the MTD and/or RD 	FPA150 Monotherapy 
 The incidence of AEs, clinical laboratory abnormalities, and ECG abnormalities
FPA150 Combined with Pembrolizumab 
 To evaluate the safety and tolerability of FPA150 in combination with pembrolizumab in selected 	FPA150 Combined with Pembrolizumab 
 The incidence of AEs, clinical laboratory abnormalities, and ECG abnormalities in patients

OBJECTIVES	ENDPOINTS
patients with B7-H4+ ovarian cancer treated at the MTD and/or RD	treated with FPA150 in combination with pembrolizumab
SECONDARY - EFFICACY	

FPA150 Monotherapy
 
 • To evaluate the clinical benefit of FPA150 as monotherapy in patients with B7-H4+ advanced solid tumors treated at the MTD and/or RD 	
FPA150 Monotherapy
 
 • ORR, defined as the total number of patients with confirmed responses of either CR or PR per RECIST v1.1 divided by the total number of patients who are evaluable for a response • DOR, defined as the time from onset of response (CR or PR) that is subsequently confirmed to the first observation of progressive disease or death due to any cause • PFS, defined as the time from the patient's first dose to the first observation of progressive disease or death due to any cause)

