
FPA150 in Combination with Pembrolizumab
 
 To characterize the pharmacodynamic profile of FPA150 in combination with pembrolizumab through an analysis of the immune cell infiltrate in pre-treatment and on-treatment tumor biopsies To characterize the pharmacodynamic profile of FP150 in combination with pembroliumab through evaluation of exploratory biomarkers in peripheral blood samples 	
FPA150 in Combination with Pembrolizumab
 
 Changes in markers of tumor immune infiltrate.   Changes in selected additional pharmacodynamic biomarkers in peripheral blood samples for patients treated with FPA150 in combination with pembrolizumab
EXPLORATORY - EFFICACY	

FPA150 Monotherapy
 
 To evaluate the clinical benefit of FPA150 as monotherapy in patients with B7-H4+ advanced solid tumors treated at the MTD and/or RD 	
FPA150 Monotherapy
 
 OS, defined as time from patient's first dose to death due to any cause

FPA150 in Combination with Pembrolizumab
 
 To evaluate the clinical benefit of FPA150 in combination with pembrolizumab in patients with B7-H4+ ovarian cancer treated at the MTD and/or RD 	
FPA150 in Combination with Pembrolizumab
 
 OS, defined as time from patient's first dose to death due to any cause

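### SAP 6.3 cancels the Phase 1b secondary endpoints PFS and DOR for an unspecified data limitation, and leaves OS listed without an analysis; PFS at least should be restored

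*SAP*

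**What the plan says.** **Endpoints.** Protocol Table 2 and SAP Table 6 place ORR, DOR and PFS under "SECONDARY - EFFICACY" for Phase 1b, for both monotherapy and the combination. Both tables list OS as an exploratory efficacy endpoint, measured from "first dose to death due to any cause".

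**Protocol analysis.** Section 9.4.2 defines DOR and PFS. It censors patients who are alive and progression-free at their last tumor assessment, and states "Kaplan-Meier methodology will be used to estimate median DOR and PFS and corresponding 95% CI". It then adds "More details of censoring rule for DOR and PFS will be outlined in SAP". It gives no method for OS.

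**SAP analysis.** Section 6.3 states "Analysis and summary will not be provided for time to duration of response and progression-free" survival, and attributes this to a limitation of the data without describing it. The SAP contains no censoring rules for either endpoint. OS appears only in the objectives and the abbreviations. Section 6 has no OS analysis, and 6.3 does not mention OS. What remains is ORR with an exact CI and the best-overall-response categories (6.1), by-subject lesion, timepoint-response and new-therapy listings (6.1), an ECOG listing (6.2), and a listing of deaths under safety (7.1.6).

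**Timing.** The SAP is "Version 1.0, 1 September 2021". Section 1 says "This SAP is based on the study protocol Amendment 2 dated 04 February 2019". Protocol 6.7 says "Blinding and breaking the blind are not applicable as this study is open label".

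**The concern.** Followed as written, the SAP leaves part of the Phase 1b secondary efficacy objective unanswered. The one-phrase reason does not let a reader judge whether that was necessary.

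The loss matters because Protocol 2.1 argues unmet need largely from time-based figures: a median time to progression of 4.9 months and OS of 15.2 months in pretreated breast cancer, PFS of 4.2 and OS of 10.5 months in endometrial cancer, and PFS of 3 to 6 and OS of 13 to 16 months in ovarian cancer. A report with no PFS or OS summary cannot be set beside any of these. The gap is greatest if response rates are low, because ORR then says little about how long patients went without progression.

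**Working it through.** **1. Endpoint by endpoint, Phase 1b**

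| Endpoint | Status (SAP Table 6) | Method in Protocol 9.4.2 | Analysis in SAP | Mentioned in SAP 6.3 |
|---|---|---|---|---|
| ORR | secondary | yes | yes (6.1) | no |
| DOR | secondary | Kaplan-Meier median, 95% CI | none | yes, cancelled |
| PFS | secondary | Kaplan-Meier median, 95% CI | none | yes, cancelled |
| OS | exploratory | none given | none | no |

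Two of the three secondary endpoints are cancelled openly. One exploratory endpoint has no analysis and no statement. This applies to four planned cohorts of up to 30 patients, so to at most 4 × 30 = 120 patients. Actual enrolment is not in the documents.

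**2. Does a data limitation reach PFS?**

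- DOR exists only for responders. With very few, a median is uninformative or cannot be estimated.
- PFS needs no responders. Each dosed patient contributes a progression or death date, or a censoring time.
- SAP 6.1 closes the best-response window at the earliest of first progression, death, start of new anticancer therapy or end of study. It also imputes partial new-therapy dates and lists every timepoint response. These are the inputs to PFS. If they are adequate for best response, they give a PFS time or a censoring time.
- SAP Section 2 places the final analysis after all patients have completed or discontinued the study, so this is not an early data cut.
- Collection was planned: scans every 6 weeks for 6 months and then every 12 weeks (Protocol 8.6.1), and survival contact every 12 weeks in Phase 1b (Protocol 8.14.1).

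**3. The nearest figure in the plan**

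No stated number supports the deletion. The plan's one relevant figure is the probability, 0.81, of stopping a cohort on at most 1 response in 16 at a true rate of 0.05:

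P(X ≤ 1) = 0.95^16 + 16 × 0.05 × 0.95^15 = 0.440 + 0.371 = 0.811.

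This reproduces. A cohort may therefore end at 16 patients, so 16 events is a relevant case as well as 20.

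**4. How wide would a Kaplan-Meier median be?**

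Assume exponential times with hazard λ, no censoring and n events. At the median m = ln 2/λ:

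- the standard error of the survival estimate is 0.5/√n, and the density is λ/2;
- so SE(m) = (0.5/√n)/(λ/2) = 1/(λ√n);
- and SE(log m) = 1/(ln 2 × √n).

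The 95% CI is the estimate times or divided by exp(1.96/(0.693 × √n)):

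| Events (assumed) | SE(log m) | Factor | CI around an estimate of 4.2 months |
|---|---|---|---|
| 20 | 0.323 | 1.88 | 2.2 to 7.9 |
| 16 | 0.361 | 2.03 | 2.1 to 8.5 |
| 10 | 0.456 | 2.45 | 1.7 to 10.3 |

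The 4.2 months is borrowed from the endometrial benchmark in Protocol 2.1 for illustration only. Sixteen events in a cohort stopped at 16 requires every patient to progress or die under observation.

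**The case against.** The case for leaving the SAP alone has real substance.

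- The removal of DOR and PFS is disclosed, in a section made for the purpose. This stands.
- The primary endpoints are safety, all analyses are descriptive (Protocol 9.3) and there is no formal testing (SAP 3.4). Uncontrolled PFS is weak evidence of benefit. This stands, and it limits the importance of the point. It does not explain why a secondary endpoint goes unreported.
- If responders are few, dropping a DOR summary is reasonable, and the timepoint-response listing lets a reader trace each responder. This largely stands for DOR.
- The intervals would be wide, about twofold either way. This is true, but 9.4.2 planned these estimates for cohorts of at most 30, and a wide interval is still a valid description.
- The documents show planned collection, not completeness. This stands. It is why the SAP should say what the limitation is.
- OS follow-up may be cut short. Protocol 4.4 ends the study once the last enrolled patient finishes the 100-day follow-up, and long-term follow-up stops at study termination. This could justify not analysing OS, but the SAP does not say so.

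A reader might infer from the late date, the open label and the data-based reason that endpoints were dropped because of their results. The documents do not support that. They do not show whether outcomes were reviewed before the decision, and SAP Section 1 says the plan is finalized before data finalization. A reader might also say that the SAP deleted a specified OS analysis. It did not, because Protocol 9.4.2 never gave one.

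**Conclusion.** The point holds and deserves a change to the SAP, though it does not touch the primary safety objectives. Two of three Phase 1b secondary efficacy endpoints, both with a method in the protocol, are cancelled for a reason that is not specified and does not plausibly extend to PFS. OS is a listed exploratory endpoint with no analysis and no statement, a gap inherited in part from the protocol.

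It would be too strong to call ORR the only efficacy information left: best-response categories are tabulated, and responses and deaths are listed. ORR is the only listed efficacy endpoint with a planned summary.

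The factors of about 1.9 and 2.0 rest on an exponential shape, no censoring and assumed event counts. They show that the estimates would be imprecise but can be reported with an interval. They do not show what this trial's data would give.

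**What to change.** Amend SAP Section 6 as follows.

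1. **PFS:** restore Kaplan-Meier median PFS with 95% CI for each Phase 1b cohort and for the combination group, as in Protocol 9.4.2. Report patients, events and censored counts. State the censoring rules that 9.4.2 left to the SAP, including new anticancer therapy and missed assessments. 9.4.2 specifies no landmark rate, so none is needed.
2. **DOR:** if responders are too few for a median, list onset, end date and censoring status for each responder.
3. **OS:** add a descriptive Kaplan-Meier summary for Phase 1b, or declare in 6.3 that OS is not analysed and why.
4. **Anything still dropped:** replace the general phrase in 6.3 with the specific limitation, giving patients, responders, events and follow-up for each cohort.

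The cost is a little programming, about one table and figure per cohort, from dates the protocol already plans to collect. There is no added patient burden. The price in interpretation is wide intervals, which should be shown as such.

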7 SAFETY ANALYSES

Unless otherwise specified, all analyses will be performed using the Safety Analysis Set.

No formal comparisons of safety endpoints are planned.

7.1 Adverse Events and Deaths

7.1.1 Adverse Event Dictionary

All AEs will be coded to SOC and PT using Medical Dictionary for Regulatory Activities (MedDRA Version 21).

7.1.2 Adverse Event Severity

Adverse events are graded for severity by the investigators using the National Cancer Institute Common Toxicity Criteria for Adverse Events (NCI-CTCAE) Version 4.03. The severity grade of events for which the investigator did not record severity will be categorized as “missing” for tabular summaries and data listings.

7.1.3 Relationship of Adverse Event to Study Drug

A treatment related AE is an AE noted as related to FPA150 or pembrolizumab by the investigator. Events for which the investigator did not record relationship to study drug will be considered related to study drug for summary purposes. However, by-subject data listings will show the relationship as missing.

7.1.4 Serious Adverse Events

Serious adverse events (SAEs) will be identified and captured as SAEs if the AEs met the definitions of SAEs that were specified in the study protocol.

7.1.5 Treatment-Emergent Adverse Events (TEAE)

A treatment-emergent AE (TEAE) is defined as an AE that was not present prior to the start date of study drug or was worsened during treatment and 28 days after permanent discontinuation of study drug. An AE that was present at treatment initiation but resolved and then reappeared and the event severity increase while the subject was on treatment is also a TEAE.

If the onset date of the AE is incomplete and the AE stop date is not prior to the first dosing date of study drug, then the month and year (or year alone if month is not recorded) of onset determine whether an AE is treatment emergent. The event is considered treatment emergent if both of the following 2 criteria are met:

- The AE onset is the same as or after the month and year (or year) of the first dosing date of study drug, and

- The AE onset date is the same as or before the month and year (or year) of the date corresponding to 28 days after the date of the last dose of study drug

An AE with completely missing onset and stop dates, or with the onset date missing and a stop date later than the first dosing date of study drug, will be considered treatment emergent. In addition, an AE with the onset date missing and incomplete stop date with the same or later month and year (or year alone if month is not recorded) as the first dosing date of study drug will be considered treatment emergent.

7.1.6 Summary of Adverse Events and Deaths

The number and percentage of subjects who experienced at least 1 TEAE will be provided and summarized by SOC, PT, and treatment group. For other AEs described below, summaries will be provided by SOC, PT, maximum severity, and treatment group

- TEAE
- TE SAE
- Summary of TEAE of Grade 3-5
- TEAE related to FPA150
- TEAE leading to FPA150 treatment discontinuation
- TEAE leading to death
- TEAE of dose limiting toxicity

A brief, high-level summary of AEs described above will be provided by treatment group and by the number and percentage of subjects who experienced the above AEs.

Multiple events will be counted only once per subject in each summary. AEs will be summarized in alphabetic order of SOC and then by PT in descending order of total frequency within each SOC. For summaries by severity, the most severe severity will be used for those AEs that occurred more than once in a subject.

In addition to the above summary tables, TEAEs will be summarized by PT only in descending order of total frequency.

All AE and recorded deaths for the safety population will be listed.

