3.2 Phase 1b Objectives and Endpoints

The objectives and endpoints for Phase 1b of the study are summarized in Table 2. Additional information regarding study assessments and procedures is provided in Section 8; statistical analysis information is provided in Section 9.

Table 2: Objectives and Endpoints: Phase 1b

OBJECTIVES	ENDPOINTS
PRIMARY - SAFETY	
FPA150 Monotherapy 
 To evaluate the safety and tolerability of FPA150 as monotherapy in patients with B7-H4+ advanced solid tumors treated at the MTD and/or RD 	FPA150 Monotherapy 
 The incidence of AEs, clinical laboratory abnormalities, and ECG abnormalities

OBJECTIVES	ENDPOINTS

FPA150 Combined with Pembrolizumab
 
 To evaluate the safety and tolerability of FPA150 in combination with pembrolizumab in selected patients with B7-H4+ ovarian cancer treated at the MTD and/or RD 	
FPA150 Combined with Pembrolizumab
 
 The incidence of AEs, clinical laboratory abnormalities, and ECG abnormalities in patients treated with FPA150 in combination with pembrolizumab
SECONDARY - EFFICACY	

FPA150 Monotherapy
 
 To evaluate the clinical benefit of FPA150 as monotherapy in patients with B7-H4+ advanced solid tumors treated at the MTD and/or RD 	
FPA150 Monotherapy
 
 ORR, defined as the total number of patients with confirmed responses of either CR or PR per RECIST v1.1 divided by the total number of patients who are evaluable for a response DOR, defined as the time from onset of response (CR or PR) that is subsequently confirmed to the first observation of progressive disease or death due to any cause PFS, defined as the time from the patient's first dose to the first observation of progressive disease or death due to any cause)

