9.4 Statistical Analyses

9.4.1 Safety Analyses

Safety analyses will be performed separately within both phases of the study and for all patients combined. Data from all patients that receive any portion of at least one dose of FPA150 as monotherapy or one dose of FPA150 in combination with pembrolizumab will be included in the safety analyses. AEs, clinical laboratory information, vital signs, ECOG performance status, weight, ECGs, and concomitant medications/procedures will be tabulated and summarized. In addition, the incidence of DLTs in Phase 1a will be summarized.

Subject incidence of AEs will be summarized overall and with separate summaries for serious AEs, AEs leading to discontinuation, AEs leading to death, and NCI CTCAE Grade 3 or higher AEs. The patients' worst grade for each preferred term will be used for the summary of AEs by CTCAE grade. Treatment-related AEs and SAEs will also be summarized similarly.

Weight and vital signs will be summarized descriptively (N, mean, SD, median, minimum, and maximum). ECOG performance status will be summarized categorically and descriptively.

Shift tables displaying patient counts and percentages classified by baseline grade and maximum grade on treatment will be provided for laboratory data by cohort and overall as appropriate.

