3 GENERAL CONSIDERATIONS

All statistical tabulations and analyses will be done using SAS[®], Version 9.3 or higher.

Unless otherwise noted, continuous variables will be summarized using the number of subjects (n), mean, standard error (SE) or standard deviation (StD), median, minimum, and maximum; categorical variables will be summarized using the number and percentage of subjects in each category.

By-subject listings will be presented for all subjects in the Safety Analysis Set and sorted by phase, treatment group, subject ID number, visit date, and time (if applicable). Data collected on log forms, such as AEs, will be presented in chronological order within the subject. The treatment group to which subjects were enrolled will be used in the listings. Age, sex at birth, race, and ethnicity will be included in the listings, as space permits.

The summaries of the efficacy data will be presented by treatment group.

Unless stated otherwise, summaries will be provided separately for the following 3 groups of subjects:

- Phase 1a (Dose Escalation + Exploration)
- Phase 1b (Monotherapy)
- Phase 1a (Combination Safety Lead-in) and Phase 1b (Combination)

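### SAP 7.1.6 limits the combination group's relatedness and discontinuation tables to FPA150, and omits for every group the treatment-related SAE summary planned in protocol 9.4.1

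*SAP*

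**What the plan says.** Protocol 9.4.1 plans, beyond overall AE incidence, "separate summaries for serious AEs, AEs leading to discontinuation, AEs leading to death", together with a summary of events of Grade 3 or higher. It then adds: "Treatment-related AEs and SAEs will also be summarized similarly". Neither sentence is restricted to one drug.

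SAP 7.1.6 lists the AE tables to be produced. The only relatedness table is "TEAE related to FPA150" and the only discontinuation table is "TEAE leading to FPA150 treatment discontinuation". Serious events appear once, as all treatment-emergent SAEs whatever their cause. SAP 7.1.3 nevertheless defines relatedness for both drugs: "A treatment related AE is an AE noted as related to FPA150 or pembrolizumab by the investigator".

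SAP section 3 reports three groups separately, one of which pools the Phase 1a combination lead-in with the Phase 1b combination cohort. Protocol 6.5 lets a combination patient stop one drug and continue the other.

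The SAP's section on departures from the protocol, 6.3, is headed "Changes from Protocol-Specified Efficacy Analysis" and covers no safety analysis.

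On SAEs arising after the end-of-treatment visit, protocol 8.12.1 asks for reports only when the investigator suspects FPA150. Protocol 8.12.6 asks for them when the study treatment is suspected.

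**The concern.** One primary objective of Phase 1b is "To evaluate the safety and tolerability of FPA150 in combination with pembrolizumab in selected patients with B7-H4+ ovarian cancer", and Phase 1a has a matching one. The protocol expects immune-related events with this combination (4.1.2.2.2). A reader of the study report will look for how many combination patients had an event judged related to the regimen, how many of those events were serious, and how many patients gave up either drug because of an event. As listed, SAP 7.1.6 answers none of these in full. An event attributed to pembrolizumab alone, or one that ends pembrolizumab alone, falls outside the two tables meant to hold such events. The tables would then understate the burden of the regimen without signalling it. The missing related-SAE table touches monotherapy patients as well.

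The late-SAE wording is a separate matter, of reporting rather than tabulation. A site treating combination patients finds sections that do not agree on which late events to send to the sponsor.

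**Working it through.** The check is mainly a comparison of texts.

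**Step 1. The three affected summaries.**

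| Summary | Protocol 9.4.1 | SAP 7.1.6, combination group | SAP 7.1.6, monotherapy groups |
|---|---|---|---|
| Treatment-related AEs | Planned, no drug named | FPA150 only | Matches, since FPA150 is the only drug |
| AEs leading to discontinuation | Planned, no drug named | FPA150 only | Matches |
| Treatment-related SAEs | Planned | Absent | Absent |

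The third row reads the protocol's last sentence as related AEs and related SAEs. That is the natural reading, because the same paragraph has already planned a summary of all serious AEs. The all-causality tables (TEAE, SAE, Grade 3-5, death) and the listing of all AEs and deaths do carry over.

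**Step 2. Follow a patient through the tables.**

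- A combination patient has a TEAE attributed only to pembrolizumab. SAP 7.1.3 makes it treatment-related. It enters the all-causality tables but no relatedness table.
- A combination patient stops pembrolizumab for a TEAE and stays on FPA150, as protocol 6.5 allows. The event enters no TEAE discontinuation table. SAP 7.1.3 does not bear on this; the departure is from protocol 9.4.1 alone.
- Any patient has an SAE related to FPA150. It is counted in the SAE table without its cause and in the FPA150-related table without its seriousness. No table combines the two.

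**Step 3. Does the case report form permit these tables?** The documents do not settle this. Protocol 8.12.3.3 poses one causality question about the study treatment, and 8.12.3.4 gives one action-taken list. The wording of SAP 7.1.3 suggests attribution by drug but does not establish it.

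- If attribution and action were recorded by drug, the gaps in step 2 occur as described.
- If they were recorded once for the regimen, an FPA150-only table cannot be produced for combination patients. What can be produced is an any-treatment table, and the SAP's label would be wrong.

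The SAP text needs correcting in either case.

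**Step 4. What else covers the gap?** Disposition with reasons (SAP 4.1), dose delay or interruption with reasons (SAP 4.2), and the rule that lead-in pembrolizumab modifications for related toxicity count as DLTs (protocol 6.4.5) give partial cover. None is a relatedness table or a TEAE discontinuation table, and the DLT rule applies to the lead-in only.

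**Step 5. Size.** From protocol 9.1, the lead-in has 6 to 22 patients and the combination expansion cohort up to 30. Ceiling: 22 + 30 = 52 patients in named combination cohorts.

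**Step 6. Late SAEs in combination patients.**

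| Protocol section | Scope |
|---|---|
| 8.12.1 | Post-EOT SAEs, only if related to FPA150 |
| 8.12.6 | Post-EOT SAEs, if related to the study treatment |
| 8.12.4 | Deaths or AEs at any time after the patient has discontinued or terminated participation, if reasonably related to the study |

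The meaning of study treatment is itself unsettled. Protocol 8.12.2 glosses it as FPA150, Table 9 lists both drugs under that column heading, and the minimum SAE report content in 8.12.6 allows for more than one study treatment. An SAE attributed only to pembrolizumab is out of scope under 8.12.1, in scope under 8.12.6 if Table 9 governs, and in scope under 8.12.4 once the patient has left the study.

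**The case against.** The best reply is that nothing essential is lost. The primary endpoint for the combination is the incidence of AEs regardless of cause, and that stays fully tabulated and listed. The study is open-label, descriptive and without a control arm, so attribution tables are supportive. That stands, and it limits the weight of the point. A reader might infer that the combination's primary safety endpoint goes unreported; the documents do not support that.

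A reader might also infer, from the silence of SAP 6.3 on safety, that the sponsor has breached a duty to declare the change in the SAP. That does not follow. The opening of protocol section 9 places the description and justification of deviations in the final study report, and 9.3 requires an amendment only when a principal feature changes. The departures still have to be recognised before they can be described there.

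FPA150 is the investigational drug, so an FPA150-specific table has its use. It can stand beside an either-drug table, but it does not replace the summary that protocol 9.4.1 plans.

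On late SAEs, one might conclude that a pembrolizumab-attributed event would go unreported whenever a site follows 8.12.1. Protocol 8.12.4 weakens that, because its scope after a patient leaves the study is not tied to FPA150. It does not remove the restriction in 8.12.1. The matter also barely touches the disputed tables: the SAP's TEAE window closes 28 days after study drug is stopped (7.1.5), and footnote s of the protocol's Schedule of Assessments ends AE collection at the Day 28 follow-up visit.

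**Conclusion.** The point holds as an inconsistency between SAP and protocol, and for relatedness also within the SAP. For the combination group, two summaries are narrower than protocol 9.4.1. For every group, the treatment-related SAE summary is missing.

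The figure of 52 is a planning ceiling, not an enrolment count, and it covers only the named cohorts. How many events would be left out cannot be computed from the documents, so the size of any understatement is unknown. The wording mismatch is certain. Its consequence for the two narrowed tables depends on whether the case report form recorded attribution and action by drug. The related-SAE gap does not depend on that, but it does rest on the reading of protocol 9.4.1 given above.

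The conflict among protocol 8.12.1, 8.12.4 and 8.12.6 is real and separate. The passages must be reconciled; no view is taken here on which reporting scope is right.

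**What to change.** In SAP 7.1.6, for the combination group, tabulate TEAEs related to either drug, treatment-emergent SAEs related to either drug, and TEAEs leading to discontinuation of either drug. Add by-drug versions only if the case report form recorded attribution and action taken by drug. For the monotherapy groups, add treatment-emergent SAEs related to FPA150. If any of these tables stays out, describe and justify the omission in the study report, as protocol section 9 requires.

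The cost is two table definitions widened for one reporting group and one table added for all groups, from AE data already collected.

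Separately, reconcile protocol 8.12.1, 8.12.4 and 8.12.6 for combination patients, and define study treatment consistently across 8.12.2 and Table 9. This is a wording change. If follow-up is already complete, one sentence in the study report stating which scope was applied would do.
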